Urine samples were collected using a standardized protocol (Lithotest®, Biohealth, Turin, Italy), and the metabolic profile was examined in an external certified lab (Lithocenter, Turin, Italy). Briefly, during collection, 24-hour (24 h) urine was aliquoted into two fractions to which 10 mL hydrochloric acid (to prevent calcium/phosphate precipitation) and 1 mL Hibitane (to prevent bacterial contamination) were added. The acidified aliquot was used to quantify calcium (Ca), citrate, magnesium (Mg), oxalate, phosphate (PO₄) and sulphate (SO₄); the Hibitane aliquot was tested for ammonium, chloride (Cl), creatinine, pH, potassium (K), sodium (Na), urea, and urate. In addition, a sample of fasting-morning urine was collected within 2 h after the 24 h collection ended, and was analyzed for citrate, calcium, urate (all expressed as creatinine ratios) and pH. Reference values were established on the basis of the assessment of mineral metabolic profile to evaluate the lithogenic risk [2,3,4]. The renal acid load was determined by calculating the 24 h urinary “potential renal acid load” (uPRAL) as follows [5]:

$$[\text{Cl (mmol day}^{-1}) + \text{SO}_4 \text{ (mmol day}^{-1}) \times 2 + \text{PO}_4 \text{ (mmol day}^{-1}) \times 1.8] - [\text{Na (mmol day}^{-1}) + \text{K (mmol day}^{-1}) + \text{Mg (mmol day}^{-1}) \times 2 + \text{Ca (mmol day}^{-1}) \times 2]$$

5. Immunoenzymatic Assay of BTM

The serum level of the bone turnover markers (BTMs) was evaluated at baseline and after 3 and 6 months of treatment. The BTM assay was carried out by following the recommended actions to minimize the pre-analytical variability [6]. The blood samples were collected after overnight fasting (between 08:00 and 10:00 a.m.), centrifuged within 2 h from collection, at 1000 g min⁻¹ for 15 min and at room temperature. The serum was transferred into cryotubes (0.5 mL of serum per cryotube)

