All calculations and analyses were carried out using StatView 5.01 for Windows (SAS Institute Inc., Cary, NC, USA) and MedCalc Statistical Software version 18.2.1 (MedCalc Software bvba, Ostend, Belgium). The sample size calculation was based on a previous randomized clinical trial (RCT) aimed to evaluate the effect of K citrate on calcium metabolism and BTM in a cohort of individuals (males and females, age >55 years) treated for 6 months [7]. The present RCT was powered considering a Type I error (α) = 0.05 (two-sided), and Type II error (β) = 0.20 (power is 80%). Fifteen patients per group were sufficient, but the expected proportion of dropouts was 20%; therefore, as a precaution, 20 women in each group were recruited. Quantitative data were expressed as the arithmetic mean plus or minus the standard error of the mean (mean \pm SEM). The D'Agostino-Pearson method was used

to test the normality assumption of continuous variables, and a *log* transformation was applied when the data distribution was non-normal. The data analysis was carried out following intention-to-treat principles. All follow-up parameters were analyzed using a “last value carried forward” approach under the intention-to-treat principle in order to address missing data [8]. The effect of K citrate on BTMs and blood/urine analytes was evaluated by applying the *t*-test, with comparison within the groups (paired analysis of the effect of treatment over time), and between the groups (independent comparison between K citrate and the placebo at the same time point). In order to highlight the changes over time, the results were expressed in line-graphs as deviations from the value observed before treatment, i.e., $[(\text{BTM concentration at time point} \times \text{BTM concentration at baseline}^{-1}) - 1]$ Thus, obtaining a baseline value equal to zero. The degree of association between the continuous variables was calculated by measuring the Pearson correlation coefficient. Differences and correlations were considered to be statistically significant when the *p* value was <0.05 .

References

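### Carry-forward is the only missing-data method with 20% dropout expected; it can bias the 6-month arm contrast in either direction and distort the paired tests, and no planned analysis would show it

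*Combined protocol and SAP*

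**What the plan says.** Section 6 (Calculations and Statistical Analysis) states: "The data analysis was carried out following intention-to-treat principles". For all follow-up parameters it then uses a "last value carried forward" "approach under the intention-to-treat principle in order to address missing data", citing a methods paper (reference 8). It does not say why a woman's values would stay unchanged after she leaves, or whether baseline is carried for a woman lost before month 3.

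On numbers it says "Fifteen patients per group were sufficient" and that "the expected proportion of dropouts was 20"%, so 20 per group were recruited.

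The effect is assessed by t-tests of two kinds: a "paired analysis of the effect of treatment over time" within each arm, and an "independent comparison between K citrate and the placebo at the same time point". Line graphs of relative change and Pearson correlations complete the plan. Section 5 says that the serum marker level "was evaluated at baseline and after 3 and 6 months of treatment"; section 2 gives the same visit schedule for blood and urine.

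**The concern.** There is one visit between baseline and month 6. A woman lost after month 3 contributes her 3-month value as a 6-month result. A woman lost earlier contributes, if intention to treat is followed literally, a value from before treatment. The t-tests treat both as observed.

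The arm contrast can be wrong in several ways:
- It moves toward zero if the effect is still growing after the carried visit, or if women leave before month 3.
- It moves away from zero if the effect wanes after month 3.
- It moves in either direction if the number of dropouts, their timing or their relation to outcome differs by arm.

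The paired tests have less protection, because a change common to both arms does not cancel within one arm. Such a change is possible here: the eligibility text excludes users of calcium supplements and vitamin D, and section 2 then gives both to every woman. The documents do not give its size.

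At stake is whether the 6-month results describe treatment or partly describe who left, when and from which arm. All planned tests of follow-up values use the carried data, so none would separate the two.

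**Working it through.** **Inputs from section 6:** 15 per group required, 20% dropout, 20 per group recruited, two-sided alpha 0.05, power 80%. **Visits (sections 2 and 5):** baseline, 3 and 6 months. **Assumed, because not in the documents:** effect size and time course, drift, dropout pattern, SD of 1, and correlation between visits of 0.5 or 0.7. Early dropout means that baseline is carried; late means that the 3-month value is carried. Rates come from simulation with 20 women per arm. Where two figures are joined by a slash, they are for correlations 0.5/0.7.

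**1. The plan's figure.** 15/(1 − 0.20) = 18.75, so 19; the plan rounds up to 20 as a precaution, which is consistent. Expected carried values: 20 × 0.20 = 4 per arm, leaving 16 completers. The base of 15 cannot be reproduced without an effect size. Solving backwards (noncentral t, 15 per group, 80% power) gives 1.06 SD. At 1.06 SD, power is 82.6% with 16 per group and 90.4% with 20.

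**2. General bias.** Bias in the 6-month contrast = pK × eK − pP × eP. Here p is the share of women carried in the K citrate (K) or placebo (P) arm, and e is the mean of carried minus true 6-month value among them. It is zero only when the two products are equal.

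**3. Dropout at random, same number and timing in both arms.** Bias = −[pE × D6 + pL × (D6 − D3)], where pE and pL are the shares lost early and late, and D3 and D6 the effects at months 3 and 6.

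| Dropouts per arm | D3 | D6 | Bias (SD) | Share of effect retained | Rejection rate, raw t-test |
|---|---|---|---|---|---|
| 4 early | any | 1.06 | −0.20 × 1.06 = −0.21 | 80% | 71% |
| 2 early, 2 late | 0.53 | 1.06 | −(0.106 + 0.053) = −0.16 | 85% | 77% to 78% |
| 2 early, 2 late | 1.06 | 1.06 | −0.11 | 90% | 82% |
| 4 late | 0.53 | 1.06 | −0.20 × 0.53 = −0.11 | 90% | 83% |
| 4 late | 1.06 | 1.06 | 0 | 100% | 90% to 91% |
| 4 late | 1.06 | 0 | +0.20 × 1.06 = +0.21 | none to retain | about 8.5% |

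The last row is a waning effect: the true 6-month difference is zero, so 8.5% is a false-positive rate for that visit. A completer t-test in the first five rows has 82% to 83% power.

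**4. No treatment effect, 1 SD shift in both arms by month 3.** Absolute bias = difference in early-dropout share × 1 SD. For 25% v 15% early: 0.10 × 1 = 0.10 SD. If each woman leaves at random at these rates, Type I error is about 6%; at 20% v 20% it is about 5%. If the counts are instead fixed at 5 v 3, it is about 4%, but fixing counts makes the test conservative (4 v 4 gives 3.5% to 3.7%). In the extreme case of 4 early in one arm and 4 late in the other, bias is 0.20 SD and Type I error about 8%.

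**5. Dropout related to outcome.** No effect, no drift, 4 of 20 lost late per arm, leaving at random in one arm.
- *Highest 3-month values leave in the other arm.* Absolute bias is 0.13/0.08 SD for carry-forward and 0.17/0.23 SD for a completer t-test. It is about zero for a mixed model without baseline, because this dropout depends only on an observed value.
- *Highest unseen 6-month values leave in the other arm.* Absolute bias is 0.13/0.08 SD for carry-forward and about 0.25/0.19 SD for the same mixed model.

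**6. Paired test.** A true 1 SD within-arm change with 4 of 20 lost early is reported as 0.80 × 1 = 0.80 SD. If the highest 3-month values leave in both arms, the arm contrast is about unbiased but each arm shows a spurious change of 0.13/0.08 SD.

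**The case against.** Section 6 states its method, cites a source for it and applies it to everyone randomized. Lost numbers are already allowed for: 20 recruited, about 16 expected to complete, 15 needed. Every bias figure rests on assumed drift, time course or selection. The favoured alternative also depends on an untestable assumption and did worse than carry-forward when dropout depended on the unseen 6-month value.

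Much of this stands. A reader might infer that the trial's result is biased, that false positives are inflated, or that power falls below 80%. The documents support none of these as fact, since they give no dropout by arm or timing and no effect size. Power need not fall: when all dropouts are late and the effect is full by month 3, carry-forward has 90% against 84% to 86% for a mixed model without baseline adjustment.

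The opposite inference, that carry-forward is safely conservative, is not supported either, because a waning effect or unequal dropout can push the contrast away from zero. Nor does it follow that a mixed model removes the problem.

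What the objection does not answer is that the plan has a single analysis resting on values staying fixed after dropout, with nothing to test a reader's trust in it.

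**Conclusion.** The concern holds in conditional form. Bias in the 6-month contrast is possible in either direction, and the plan cannot detect it. There is none if dropout is unrelated to outcome, equal in number and timing in both arms, and either treatment has no effect at any visit or the effect is full by month 3, stays so, and all dropouts come later. In the middle cases the size is modest: up to 20% attenuation of an assumed 1.06 SD effect, or 0.10 SD of artefact. About 0.2 SD away from the truth under a null 6-month effect needs a fully waned effect or sharply different dropout timing. The paired tests can mislead even where the arm contrast does not. The argument is bias and transparency, not power. This is a worthwhile, inexpensive improvement, not a fatal flaw. Confidence is medium, because all sizes depend on quantities that the documents do not give.

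**What to change.** - **Main analysis:** a likelihood-based mixed model for repeated measures on all randomized women, using the 3- and 6-month values (log scale where the plan already uses it). Include baseline as a covariate or constrain it equal across arms, with arm-by-visit terms, unstructured covariance and a small-sample degrees-of-freedom correction. Report the 6-month arm contrast.
- **Within-arm changes:** take them from the same type of model with baseline included as an outcome, in place of paired tests on carried values.
- **Sensitivity analysis:** keep carry-forward, and state whether baseline is carried for women lost before month 3.
- **Reporting:** give dropouts by arm and timing. This alone would let a reader judge the exposure.

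Cost: SAP wording, some added analysis work and possibly other software; no new data. The model assumes missing at random and can be more biased than carry-forward if dropout depends on the unseen 6-month value, which is why both analyses should be shown. Any power gain should not be credited to the missing-data method alone: in the same illustrations, with baseline adjustment, carry-forward has 88% to 99% power and the mixed model 90% to 98%.

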A randomized, double-blind, placebo-controlled, parallel-group study, with balanced randomization (1:1) was designed. The study was approved by the local research committee and registered at Clinical Trial Gov (ID: NCT02731820). The participants were recruited from a cohort of postmenopausal women treated at the Radiodiagnostic Unit of Rizzoli Orthopedic Institute (IOR) from January 2016 to June 2017; periodic measurements of lumbar (at the L2–L4 level) and femoral BMD were carried out using dual-energy X-ray absorptiometry (DXA) (Discovery DXA System, Hologic Inc., Bedford, MA, USA). Written informed consent was obtained from all participants. A code was assigned to each woman at the beginning of the trial which was used to track the data throughout the study. The inclusion criteria were women with osteopenia (T-score <-1 and >-2.5) and more than 5 years post-menopause. The risk of fracture was evaluated by using the FRAX® tool [1] based on an algorithm that takes into account demographic characteristics, medical history, some clinical risk factors as well as bone mineral density (BMD) at the femoral neck. The exclusion criteria were risk of fracture (FRAX: >20 major osteoporotic fractures; >3 hip fractures), hyperkalemia, renal insufficiency, urolithiasis, use of therapies influencing bone metabolism (e.g., corticosteroids, aromatase inhibitors and estrogens), use of drugs (such as diuretics and proton pump inhibitors), calcium and potassium supplements, vitamin D, current or recent (less than three years prior to the start of the study) use of bisphosphonates, gastrointestinal disorders which hamper nutrient absorption, and mental or psychiatric disorders which precluded the possibility of correctly adhering to the protocol. All the women were interviewed regarding food habits; they followed their usual diet throughout the duration of the study. Participants were assigned to the treatment or the placebo group using a randomization sequence created by independent personnel (IOR pharmacy) using a free online tool (<http://randomization.com>) and were stratified with a 1:1 allocation using a random block size of 4.

2. Supplements

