The K citrate and the placebo were kindly provided by a manufacturer (Biohealth, Turin, Italy). They were in tablet form, identical in appearance, and were packaged in bottles which were rendered anonymous (A and B) until the end of the study. The products were stored at the IOR pharmacy and dispensed according to the computer-generated randomization list. Each woman received the supplements in the corresponding prepacked bottle. Both the subjects and the investigators who followed up the participants were blinded to group assignment. All subjects had daily supplementation with vitamin D3 cholecalciferol (400 IU day $^{-1}$) and calcium carbonate (500 mg

day⁻¹). The participants assigned to the experimental group received 30 mEq K citrate daily in two tablets for oral administration; those assigned to the placebo group received the same quantity of tablets containing only the excipients. The participants had clinic visits at the time of randomization (baseline), and at 3 and 6 months. At each time point, they underwent blood and urine evaluations. The laboratory staff performing the assays was unaware of the source of the samples which were identified by numeric codes.

3. Blood Analyses

Fasting venous blood samples were collected and analyzed for creatinine, sodium, potassium, total calcium, inorganic phosphate, parathyroid hormone (PTH), and 1,25-dihydroxyvitamin D. These analytes were measured by routine methods.

4. Urine Analyses

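### The effect of K citrate is judged by within-arm paired t-tests as well as by the randomised comparison, and the plan does not say which one decides

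*Combined protocol and SAP*

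**What the plan says.** The relevant text is in section 6, Calculations and Statistical Analysis. It opens with the purpose: "The effect of K citrate on BTMs and blood/urine analytes was evaluated by applying the" t-test. Two kinds of test then serve that one purpose:

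- within each arm: "comparison within the groups (paired analysis of the effect of treatment over time");
- between arms: "and between the groups (independent comparison between K citrate and the placebo at the same time point").

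A single decision rule follows: "Differences and correlations were considered to be statistically significant when the" p value is below 0.05. No section names a primary comparison, ranks the between-arm test above the paired tests, or calls the paired tests descriptive.

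Two statements elsewhere bear on how a within-arm change can be read. Section 2, Supplements, says: "All subjects had daily supplementation with vitamin D3 cholecalciferol" and calcium carbonate, so the placebo arm receives both. The exclusion list in the opening section on design and eligibility includes use of "calcium and potassium supplements, vitamin D, current or recent" bisphosphonates.

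**The concern.** The trial has a placebo arm so that changes unrelated to K citrate can be subtracted. A paired test in the K citrate arm makes no use of that arm. Its null hypothesis is that nothing changed between baseline and follow-up, which is not the hypothesis that K citrate does nothing. Natural drift, regression to the mean and the effect of any co-treatment can all reject it.

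Co-treatment is a real candidate here. Everyone receives calcium and vitamin D, and women already using them were excluded, so the supplements were probably new at entry. That is an inference, because no start date or run-in is stated. The argument does not depend on it: any shared change over time has the same consequence.

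The wording adds to the risk. The paired test is the one described as showing the effect of treatment. The line graphs show deviation from each woman's own baseline, whereas the planned between-arm test compares values at a given visit. The only test of change that the plan specifies is therefore the within-arm one. If that test is significant and the between-arm test is not, the plan gives no rule for the conclusion, and a change that also occurred on placebo could be reported as an effect of K citrate.

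**Working it through.** **The plan's own figures.** Section 6 gives "Type I error (α) = 0.05 (two-sided), and Type II error (β) = 0.20 (power is 80"%), with 15 per group sufficient, 20% dropout expected and 20 per group recruited.

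- Dropout step: 15 / (1 − 0.20) = 18.75, so 19. The stated 20 is consistent with this.
- The 15 per group cannot be reproduced, because no endpoint, difference or SD is given. Solving backwards with the normal approximation, a between-arm test needs a standardised difference of (1.960 + 0.842) × √(2/15) = 1.02 (1.06 with the t distribution). A paired test in one arm needs (1.960 + 0.842) / √15 = 0.72 (0.78 with the t distribution). The plan does not say which test the 15 refers to, which is the same ambiguity again.

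**Error rate of each test when K citrate does nothing.** Suppose both arms change by the same amount d, in units of the SD of within-woman change. The documents give no value for d, so a range is assumed.

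- Paired test in the K citrate arm: the statistic has a noncentral t distribution with n − 1 degrees of freedom and noncentrality d√n. Let p be the probability that it is significant at two-sided 0.05. For n = 20 and d = 0.5 the noncentrality is 0.5 × √20 = 2.24, and p = 0.56.
- Significant on K citrate but not on placebo: the arms are independent, so the probability is p(1 − p). At d = 0.3 this is 0.247 × 0.753 = 0.186.
- Between-arm test: the shared change cancels, so the error rate is 5% for every d.

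Results for n = 20 per arm, one marker and one time point:

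| Assumed shared change d | K citrate paired test significant | Significant on K citrate only | Between-arm test significant |
|---|---|---|---|
| 0 | 5% | 5% | about 5% |
| 0.1 | 7% | 7% | about 5% |
| 0.2 | 14% | 12% | about 5% |
| 0.3 | 25% | 19% | about 5% |
| 0.5 | 56% | 25% | about 5% |
| 0.8 | 92% | 7% | about 5% |
| 1.0 | 99% | 1% | about 5% |

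With 15 per arm, the paired test is significant in 11%, 19%, 44% and 82% of trials at d = 0.2, 0.3, 0.5 and 0.8. The K citrate only pattern occurs in 10%, 16%, 25% and 15%.

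**Check by simulation.** With 100,000 trials per setting and n = 20, the paired test rejects in 24.6% at d = 0.3 and 56.2% at d = 0.5, in line with the table. With 50,000 trials per setting, baseline to follow-up correlations of 0.5 and 0.7 and shifts from 0 to 1.0 SD, the between-arm test at the same time point rejects in 4.8% to 5.1%. A between-arm test on change rejects in 4.8% to 5.2%.

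**The case against.** The strongest reply is that the valid test is already in the plan. The trial is randomised and placebo-controlled, the between-arm comparison is specified, and no sentence says that a within-arm p-value alone establishes efficacy. On this view only a sentence of priority is missing. It is true that no analysis is missing. But the sentence that introduces both tests presents both as evaluating the effect of K citrate under one threshold, so a within-arm claim would comply with the plan as written.

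Second, the paired test is run in both arms, so a large shared change would usually show on placebo as well. Both arms are significant together in about 0.924² = 85% of trials at 0.8 SD and 0.989² = 98% at 1.0 SD. This stands, and the 92% and 99% rows should not carry the argument. The more deceptive pattern is K citrate significant, placebo not, and between-arm not. By simulation it occurs in about 6%, 17%, 23%, 7% and 1% of trials at 0.1, 0.3, 0.5, 0.8 and 1.0 SD. It misleads only if readers contrast the two within-arm p-values, which the plan does not say they will.

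Third, the shifts are assumed, and carrying last values forward would dilute them. In an assumed extreme where 4 of 20 women per arm have only a baseline value to carry forward, the paired rejection rate at 0.5 SD falls from about 56% to 46%. That changes the size of the problem and not its direction.

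Fourth, the planned same-visit comparison already holds its 5% error rate. This is correct: adjusting for baseline is a matter of precision and of matching the graphs, and is not needed for validity.

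**Conclusion.** The concern holds. Section 6 gives an uncontrolled before-after test the same standing as the randomised comparison, so the plan permits a change shared with placebo to be declared an effect of K citrate. If K citrate has no effect and both arms change by 0.3 to 0.5 SD, that happens in 25% to 56% of trials for a single marker and visit with 20 women per arm, against about 5% for the between-arm test. With no shared change the paired test also holds 5%, so the harm depends on how much both arms move, which the documents do not let us estimate. The rates assume normally distributed changes and complete data. The fault itself rests on the text and not on any particular shift. It should be fixed. It does not invalidate the between-arm analysis and does not change the sample size.

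**What to change.** Revise section 6 to say three things:

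- The effect of K citrate is judged only by the randomised comparison, K citrate minus placebo, reported with its 95% confidence interval.
- That comparison is preferably made on change from baseline, or with adjustment for the baseline value, so that the test matches the graphs.
- Within-arm changes are descriptive and support no efficacy conclusion, whatever their p-values. If they disagree with the between-arm result, the between-arm result stands.

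The cost is a few sentences and, if the baseline-adjusted form is adopted, re-running the comparisons on data already collected. No new measurements are needed. Some significant within-arm changes could then no longer be presented as effects of K citrate. Because the section is written in the past tense, the revision should be dated, and any report should say whether the priority was set before or after the results were known.

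### The stated between-arm t-test names no baseline adjustment; ANCOVA on the baseline already collected would lower the detectable effect at 20 per arm from 0.91 SD to 0.87–0.55 SD (assumed correlation 0.3–0.8)

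*Combined protocol and SAP*

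**What the plan says.** Section 6 evaluates the effect of K citrate with the t-test in two forms. One is paired, within each group over time. The other is an "independent comparison between K citrate and the placebo at the same time point". Only the second compares the randomized arms. No ANCOVA, change-score test or mixed model is named. Relative deviation from baseline is defined in the same section, but as the quantity drawn in the line-graphs.

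Baseline values are part of the schedule. Section 5 says the serum level of the markers "was evaluated at baseline and after 3 and 6 months of treatment". Section 2 lists visits at baseline, 3 and 6 months and adds: "At each time point, they underwent blood and urine evaluations".

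On size, section 6 gives two-sided α = 0.05, power 80%, and: "Fifteen patients per group were sufficient, but the expected proportion of dropouts was 20" per cent, so "20 women in each group were recruited". It gives no endpoint, difference or SD. Analysis is by intention to treat, with the last value carried forward. A log "transformation was applied when the data distribution was non-normal". The opening design section says participants "were stratified with a 1:1 allocation using a random block size of 4", without naming a stratification factor.

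**The concern.** As written, the baseline value enters a paired test that does not compare the arms, and a graph. It does not enter the comparison that randomization protects. This has two costs.

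- **Precision.** Differences between women that persist from baseline to follow-up stay in the error term of the unadjusted test. Baseline adjustment removes the part that baseline predicts.
- **Chance imbalance.** With 20 women per arm, some of the many analytes will differ at baseline by chance. An unadjusted comparison at 3 or 6 months carries part of that difference forward, where it can pass for a treatment effect or hide one.

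The unadjusted test is not biased, and its overall error rate is not inflated. The point is that information already collected is left out of the main comparison of a small trial.

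**Working it through.** **Inputs.** From section 6: two-sided α = 0.05, power 80%, 15 evaluable and 20 recruited per arm, 20% dropout. Assumed: correlation r between baseline and follow-up of 0.3, 0.5, 0.7 or 0.8, equal SDs and normal data on the analysis scale.

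**1. The plan's own figure.** The dropout step is consistent: 15/(1 − 0.20) = 18.75, so 19, against 20 recruited. The 15 itself cannot be reproduced without a difference and SD, so it can only be inverted.

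**2. Unadjusted t-test.** Solve for the standardized difference d at which a noncentral t with 2n − 2 df and noncentrality d√(n/2) gives 80% power.

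- n = 15 (28 df): d = 1.06 SD
- n = 20 (38 df): d = 0.91 SD

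**3. ANCOVA.** The residual SD is multiplied by √(1 − r²), and one df is lost. For example, at n = 20 and r = 0.5: 0.910 × √0.75 = 0.79.

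| r | 15 per arm | 20 per arm | Unadjusted n per arm matching 20, 20/(1 − r²) | 95% CI half-width at 20 per arm |
|---|---|---|---|---|
| no adjustment | 1.06 SD | 0.91 SD | 20 | 0.64 SD |
| 0.3 | 1.01 | 0.87 | 22 | 0.61 |
| 0.5 | 0.92 | 0.79 | 27 | 0.55 |
| 0.7 | 0.76 | 0.65 | 39 | 0.46 |
| 0.8 | 0.64 | 0.55 | 56 | 0.38 |

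Estimating the baseline slope adds an average factor of √(1 + 1/(2n − 4)), which is √(1 + 1/36) = 1.014 at n = 20. The table omits it. With it, the 20-per-arm column reads 0.88, 0.80, 0.66 and 0.55 SD. At r = 0 this factor is the whole effect, a loss of about 1%.

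**4. Change scores, for comparison.** The factor is √(2(1 − r)). At n = 20 this gives 1.08, 0.91, 0.70 and 0.57 SD for the four correlations. That is worse than the unadjusted test below r = 0.5 and weaker than ANCOVA at each of these values.

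**5. Chance imbalance.** The difference between baseline means has SD √(2/n), in units of the outcome SD: 0.316 at n = 20 and 0.365 at n = 15. The probability that it exceeds 0.5 SD in either direction is 11.4% and 17.1%. Sections 3 to 5 list about 30 quantities: 4 markers, 7 in blood, 14 in 24 h urine, uPRAL and 4 in fasting urine. The expected number beyond 0.5 SD is 30 × 0.114, about 3. This expectation holds even if the analytes are correlated.

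**6. Simulation under a true null, 20 per arm.** Overall type I error was about 5% for both tests. Among trials with a baseline difference above 0.5 SD:

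| r | t-test rejects | ANCOVA rejects |
|---|---|---|
| 0.3 | 8% | 5% |
| 0.5 | 14% | 5% |
| 0.7 | 22% | 5% |
| 0.8 | 28% | 5% |

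At a true effect of 0.91 SD, power is 80% for the t-test and about 83%, 89%, 97% and 99.5% for ANCOVA.

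**The case against.** The strongest case is that this is an efficiency gain, not an error, and that its size rests on a correlation the document does not give. Both are true. The gain runs from a few per cent at r = 0.3 to 40% at r = 0.8. The high conditional rejection rates are offset by lower ones when the arms are balanced.

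Second, section 6 does not say outright which quantity the between-arm t-test was run on. The relative deviation from baseline is defined in the next sentence, and a test on it is not excluded. The text ties that quantity to graphs only, so the raw or logged follow-up value is the more natural reading. On the other reading, ANCOVA gains less at high r (0.57 to 0.55 SD at r = 0.8 against a simple change score) and more at low r.

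Third, 0.91 SD assumes that all 20 women per arm contribute the full treatment effect. If the expected 20% left before month 3 and their baseline were carried forward (section 6 does not say), the effect would shrink by a fifth and the detectable difference would be about 0.909/0.8 = 1.14 SD. With 16 completers per arm it would be 1.02 SD unadjusted and 0.98 to 0.61 SD by ANCOVA over r = 0.3 to 0.8. The absolute figures move; the advantage of ANCOVA does not.

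Finally, the text is in the past tense, so a prespecified change may no longer be possible. That affects how the analysis is labelled, not whether it is worth doing.

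**Conclusion.** The concern holds. The only stated comparison between arms names no baseline adjustment, although baseline values are scheduled for every analyte. At 20 per arm, ANCOVA would lower the detectable effect from 0.91 SD to between 0.87 SD (r = 0.3) and 0.55 SD (r = 0.8), or from 0.88 to 0.55 SD after the slope penalty. It would also remove the effect of chance imbalance on the test. The figures assume the stated range of r, normal data on the analysis scale and all 20 per arm analysed, and they apply to each test separately because section 6 names no primary endpoint. They do not show that the trial is underpowered, nor that the t-test is invalid. This should be fixed because the likely benefit is material and the worst case, r = 0, costs about 1% of precision.

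**What to change.** At each visit, make the main between-arm analysis an ANCOVA of the follow-up value on arm and baseline value.

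- Log both values where the plan's log rule applies. Keep pH and uPRAL on the natural scale: pH is already logarithmic and uPRAL can be negative.
- Add the stratification factor if one was used, and name it.
- Report the adjusted difference, or the ratio for logged analytes, with its 95% CI.
- If the data are already unblinded, label the ANCOVA post hoc and show it beside the planned t-test for every analyte.
- State on which quantity the t-test is run.
- As a separate clarification, add to the sample-size text that 15 per arm gives 80% power for a between-arm difference of about 1.06 SD with the unadjusted test. Mark this as back-calculated, since the document does not say which contrast the 15 was sized for.

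The cost is one degree of freedom per model and some re-analysis. No further patients or measurements are needed.
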